6.3.5 Evaluation of Target Lesions

Complete Response (CR): Disappearance of all target lesions. Any pathological lymph nodes (whether target or non-target) must have reduction in short axis to <10 mm.

Partial Response (PR): At least a 30% decrease in the sum of the diameters of target lesions, taking as reference the baseline sum diameters.

Progressive Disease (PD): At least a 20% increase in the sum of the diameters of target lesions, taking as reference the smallest sum on study (this includes the baseline sum if that is the smallest on study). In addition to the relative increase of 20%, the sum must also demonstrate an absolute increase of at least 5 mm. (Note: the appearance of one or more new lesions is also considered progressions).

Stable Disease (SD): Neither sufficient shrinkage to qualify for PR nor sufficient increase to qualify for PD, taking as reference the smallest sum diameters while on study.

6.3.6 Evaluation of Non-Target Lesions

Complete Response (CR): Disappearance of all non-target lesions and normalization of tumor marker level. All lymph nodes must be non-pathological in size (<10 mm short axis).

Note: If tumor markers are initially above the upper normal limit, they must normalize for a patient to be considered in complete clinical response.

Non-CR/Non-PD: Persistence of one or more non-target lesion(s) and/or maintenance of tumor marker level above the normal limits.

Progressive Disease (PD): Appearance of one or more new lesions and/or *unequivocal progression* of existing non-target lesions. *Unequivocal progression* should not normally trump target lesion status. It must be representative of overall disease status change, not a single lesion increase.

Although a clear progression of “non-target” lesions only is exceptional, the opinion of the treating physician should prevail in such circumstances, and the progression status should be confirmed at a later time by the review panel (or Principal Investigator).

6.3.7 Evaluation of Best Overall Response

The best overall response is the best response recorded from the start of the treatment until disease progression/recurrence (taking as reference for progressive disease the smallest measurements recorded since the treatment started). The patient's best response assignment will depend on the achievement of both measurement and confirmation criteria.

For Patients with Measurable Disease (i.e., Target Disease)

Target Lesions	Non-Target Lesions	New Lesions	Overall Response	Best Overall Response when Confirmation is Required*
CR	CR	No	CR	≥ 4 wks. Confirmation**
CR	Non-CR/Non-PD	No	PR	
CR	Not evaluated	No	PR	
PR	Non-CR/Non-PD/not evaluated	No	PR	≥ 4 wks. Confirmation**
SD	Non-CR/Non-PD/not evaluated	No	SD	Documented at least once ≥ 4 wks. from baseline**

Target Lesions	Non-Target Lesions	New Lesions	Overall Response	Best Overall Response when Confirmation is Required*
PD	Any	Yes or No	PD	no prior SD, PR or CR
Any	PD***	Yes or No	PD	
Any	Any	Yes	PD	

* See RECIST 1.1 manuscript for further details on what is evidence of a new lesion.
** Only for non-randomized trials with response as primary endpoint.
*** In exceptional circumstances, unequivocal progression in non-target lesions may be accepted as disease progression.
Note: Patients with a global deterioration of health status requiring discontinuation of treatment without objective evidence of disease progression at that time should be reported as “*symptomatic deterioration*.” Every effort should be made to document the objective progression even after discontinuation of treatment.

For Patients with Non-Measurable Disease (i.e., Non-Target Disease)

Non-Target Lesions	New Lesions	Overall Response
CR	No	CR
Non-CR/non-PD	No	Non-CR/non-PD*
Not all evaluated	No	not evaluated
Unequivocal PD	Yes or No	PD
Any	Yes	PD

* ‘Non-CR/non-PD’ is preferred over ‘stable disease’ for non-target disease since SD is increasingly used as an endpoint for assessment of efficacy in some trials so to assign this category when no lesions can be measured is not advised

6.3.8 Duration of Reponses

Duration of overall response: The duration of overall response is measured from the time measurement criteria are met for CR or PR (whichever is first recorded) until the first date that recurrent or progressive disease is objectively documented (taking as reference for progressive disease the smallest measurements recorded since the treatment started).

The duration of overall CR is measured from the time measurement criteria are first met for CR until the first date that progressive disease is objectively documented.

Duration of stable disease: Stable disease is measured from the start of the treatment until the criteria for progression are met, taking as reference the smallest measurements recorded since the treatment started, including the baseline measurements.

6.3.9 Relapse Disease (after CR)/ Progressive Disease (after PR/SD)

Relapse Disease (after CR)/ Progressive Disease (after PR/SD) requires the following:

- Appearance of any new lesion more than 1.5 cm in any axis during or at the end of therapy, even if other lesions are decreasing in size. Increased FDG uptake in a previously unaffected site should only be considered relapsed or progressive disease after confirmation with other modalities. Thus, a therapeutic decision should not be made solely on the basis of the PET without histologic confirmation.

- At least a 20% increase from nadir in the SPD of any previously involved nodes, or in a single involved node, or the size of other lesions (e.g., splenic or hepatic nodules). To be considered progressive disease, a lymph node with a diameter of the short axis of less than 1.0 cm must increase by 50% and to a size of 1.5 x 1.5 cm or more than 1.5 cm in the long axis.
- At least a 50% increase in the longest diameter of any single previously identified node more than 1 cm in its short axis.

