6.3.3 Disease Parameters for RECIST criteria

Measurable disease: Measurable lesions are defined as those that can be accurately measured in at least one dimension (longest diameter to be recorded) as ≥ 20 mm by chest x-ray, as ≥ 10 mm with CT scan, or ≥ 10 mm with calipers by clinical exam. All tumor measurements must be recorded in millimeters (or decimal fractions of centimeters).

Malignant lymph nodes: To be considered pathologically enlarged and measurable, a lymph node must be ≥ 15 mm in short axis when assessed by CT scan (CT scan slice thickness recommended to be no greater than 5 mm). At baseline and in follow-up, only the short axis will be measured and followed.

Non-measurable disease: All other lesions (or sites of disease), including small lesions (longest diameter <10 mm or pathological lymph nodes with ≥ 10 to <15 mm short axis), are considered non-measurable disease. Bone lesions, leptomeningeal disease, ascites, pleural/pericardial effusions, inflammatory breast disease, and abdominal masses (not followed by CT or MRI), are considered as non-measurable.

Note: Cystic lesions that meet the criteria for radiographically defined simple cysts should not be considered as malignant lesions (neither measurable nor non-measurable) since they are, by definition, simple cysts.

‘Cystic lesions’ thought to represent cystic metastases can be considered as measurable lesions, if they meet the definition of measurability described above. However, if non-cystic lesions are present in the same patient, these are preferred for selection as target lesions.

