6.4 IMMUNE-RELATED RESPONSE CRITERIA (irRECIST)

Modified immune-related response criteria (irRECIST) will also be employed in this study. This new classification is based on the recent learning from clinical studies with cancer immunotherapies that even if some new lesions appear at the beginning of a treatment or if the total tumor burden does not increase substantially, tumor regressions or stabilizations might still occur later. For this trial, the concepts of the irRECIST are combined with RECIST 1.1. Please refer to [APPENDIX E](#) for further details.

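### PFS and duration of response have no designated progression rule, 6.3.9 adds one that conflicts with the other two and cannot be computed for nodes, and the Stage 1 response is not the primary-endpoint response

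*Combined protocol and SAP*

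**What the plan says.** **Time-to-event endpoints.** Section 6.3.11 ends PFS at relapse, progression or death and names no criteria; 10.4.2 adds none. Section 6.3.8 ends response when recurrence or progression is first objectively documented, and 6.4.1 repeats this for immune-related responses. Section 10.4.2 ends response at progression or death. No section says which definition is the one analysed.

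**Three progression rules.**
- RECIST 1.1 (6.3.5–6.3.7): the target sum rises by at least 20% and at least 5 mm over nadir, or non-target disease clearly progresses. In addition, "the appearance of one or more new lesions is also considered progressions", whatever their size. No confirmation is required.
- irRECIST: section 6.4 says these criteria "will also be employed in this study". Appendix E adds new measurable lesions to the target sum and calls progression at a 20% rise over nadir. Appendix E and 6.3.1 both require confirmation at least 4 weeks later, and 6.4.1 lets it wait up to 12 weeks.
- Section 6.3.9 opens with "Relapse Disease (after CR)/ Progressive Disease (after PR/SD) requires the following" and lists: "Appearance of any new lesion more than 1.5 cm in any axis during or at the end of therapy"; "At least a 20% increase from nadir in the SPD of any previously involved nodes, or in a single involved node", or the same rise in the size of other lesions such as hepatic nodules; a small node that "must increase by 50% and to a size of 1.5 x 1.5 cm or more than 1.5 cm in the long axis"; and "At least a 50% increase in the longest diameter of any single previously identified node more than 1 cm in its short axis".

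**What is measured.** For nodes, 6.3.3 says: "At baseline and in follow-up, only the short axis will be measured and followed".

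**Primary endpoint.** Sections 10.1.1 and 10.2 name CR plus PR by irRECIST. Partial response is a 30% decrease in diameters, and 6.3.1 requires confirmation at least 4 weeks later. The Stage 1 gate in 10.2, however, is at least 1 of 9 patients with more than a 20% reduction in tumor volume, followed by at least 3 of 17 with a positive response. The introduction to Appendix E asks for response confirmation at 6–8 weeks, while Appendix F, footnote 5, schedules the confirmatory scan at 4 weeks. Section 10.3.2 refers response classification to the whole of 6.3.

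**The concern.** Two sets of criteria can run side by side if each endpoint says which one it uses. Here PFS does not say, and the third rule agrees with neither of the others. Two analysts with the same scans could report different PFS and different duration of response, each following the protocol. Section 6.3.9 is hard to set aside, because PFS ends at relapse as well as progression and 6.3.9 is the only response section that defines relapse.

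The Stage 1 wording is a separate matter and closer to the decision. The Simon calculation needs one response event with one probability. Section 10.2 attaches the same 5% and 25% to two different events: an irRECIST response and a 20% volume reduction.

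**Working it through.** **1. The plan's own figures.** Inputs from 10.2: p0 = 0.05, p1 = 0.25, stop if 0 of 9 respond, success if at least 3 of 17 respond. With a single response definition at both stages:
- Early termination under the null: 0.95^9 = 0.630 (plan: 63%).
- Passing Stage 1 at 25%: 1 − 0.75^9 = 0.925 (plan: 92%).
- Exact type I error 0.0466 and power 0.8122, summing P(x of 9) × P(at least 3 − x of the next 8) over x ≥ 1 (plan: 5% and 80%).

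The design reproduces.

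**2. The Stage 1 event.** If lesions are spheres (assumption), a 20% volume reduction is a diameter reduction of 1 − 0.8^(1/3) = 7.2%. A 30% diameter reduction is a volume reduction of 1 − 0.7^3 = 65.7%. If volume loosely means the sum of diameters, the comparison is 20% against 30%. Either way the gate is easier to pass than a response.

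Let q be the chance under the null that a patient meets the looser event. Early termination is then (1 − q)^9. The documents do not give q; for assumed values of 0.05, 0.10 and 0.15 it is 0.630, 0.387 and 0.232.

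If the final count of 17 uses true responses, and every responder also passes the gate, the error rates are bounded by the case in which the trial never stops early. Type I error is then at most 1 − (0.95^17 + 17 × 0.05 × 0.95^16 + 136 × 0.05^2 × 0.95^15) = 0.0503. Power is between 0.812 and 0.836. Early termination is therefore the property that can move materially.

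**3. The same scans under three rules.** Illustrative cases, with an assumed target sum of 100 mm at baseline (also the nadir in the first three rows) and the bullets of 6.3.9 read as alternatives:

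| Scan | RECIST 1.1 | 6.3.9 | Appendix E |
|---|---|---|---|
| New 12 mm lesion, targets stable | PD | No (12 < 15 mm) | No: 112/100 − 1 = +12% |
| New 18 mm lesion, targets stable | PD | PD (18 > 15 mm) | No: 118/100 − 1 = +18% |
| One hepatic lesion 15 to 18 mm, rest stable | No: +3%, and 3 mm < 5 mm | PD: 18/15 − 1 = +20% | No: +3% |
| Responder at nadir 60 mm, new 11 mm lesion | PD, response ends | No | No: 71/60 − 1 = +18.3% |

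**4. Nodes.** Take SPD as the sum of products of two diameters. Suppose a node's recorded short axis goes from 16 to 18 mm (+12.5%). The unrecorded long axis decides the result:
- 24 to 22 mm: (18 × 22)/(16 × 24) − 1 = +3.1%.
- 20 to 22 mm: (18 × 22)/(16 × 20) − 1 = +23.8%.
- 18 to 27 mm: (18 × 27)/(16 × 18) − 1 = +68.8%, with the long axis up 50%.

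The short axis therefore settles neither the 20% SPD test nor the 50% longest-diameter test. The new-lesion and non-nodal tests of 6.3.9 can be computed.

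**5. Event date.** PFS does not say whether a confirmed irPD counts from the first or the confirming scan. The difference is at least 4 × 7 = 28 days and up to 12 × 7 = 84 days under 6.4.1. For duration of response, 6.3.8 and 6.4.1 do settle it: first documentation.

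**6. Response confirmation.** A scan at 28 days meets 6.3.1 and the calendar, but not the 42–56 days (6–8 weeks) of Appendix E's introduction.

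**7. Weight of one patient.** In an uncensored Kaplan-Meier estimate, one reclassified patient is 1/17 = 5.9 points, or 1/25 = 4.0 points at the accrual ceiling. The documents give no basis for a reclassification rate.

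**The case against.** The best defence is that the definitions are parallel by design: 6.3.8 belongs to RECIST, 6.4.1 to irRECIST, and 6.4 says the second is used as well. For duration of response much of this stands. Definitions exist and agree on the event date; what is missing is which one is analysed, and whether death ends a response. For PFS the defence fails, since no criteria are attached. It also does not explain 6.3.9.

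It is fair, too, that the lesion sizes above were chosen near the thresholds, and that a patient treated beyond RECIST progression is restaged after the next cycle (6.3.2). The cases show that the rules disagree, not how often.

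Three stronger readings are tempting and not supported:
- A reader might infer that all the bullets of 6.3.9 must hold together, so that a patient without an enlarged node could never progress. The first bullet counts a new lesion even while others shrink, which fits alternatives far better.
- A reader might infer that the overall response rate itself has no definition. Sections 10.1.1, 10.2 and 6.3.1 largely settle it as confirmed irCR or irPR.
- A reader might infer that the Stage 1 wording breaks the error rates. If the final count uses that response, type I error stays at or below 0.0503 and power at or above 0.812.

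**Conclusion.** The point holds. PFS has no named progression rule, duration of response has none designated, and 6.3.9 contradicts both RECIST 1.1 and Appendix E while asking for nodal measurements that 6.3.3 does not collect. The same scan can be an event or not, and a confirmed event can move by at least 28 days and up to 84. The harm is to the reproducibility of descriptive secondary results; these endpoints carry no decision rule and the sample size does not depend on them.

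Only the Stage 1 wording and the confirmation interval bear on the go/no-go decision. The four stated Simon properties are derived for one response definition and are assured as stated only if Stage 1 uses it. The 63% early-termination figure is the exposed one.

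The sizes rest on the assumed 100 mm sum, on reading the bullets of 6.3.9 as alternatives, on the sphere conversion, and on the assumed range for q.

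**What to change.** For endpoint analysis only:

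1. In 10.2, make the Stage 1 response the primary-endpoint response: confirmed irCR or irPR.
2. In 6.3.11, 6.3.8 and 10.4.2, name one rule for PFS and duration of response. Appendix E irRECIST is the consistent choice, with nodes entered by short axis. Use one label throughout in place of imRECIST, irRECIST and modified irRC. Date irPD at first documentation. State how an irPD that is never confirmed is counted, and how recurrence after irCR is counted, since a percentage rise from a nadir of zero is undefined. Make 6.3.8 and 10.4.2 agree on death. Report RECIST 1.1 as a sensitivity analysis.
3. State that the size and new-lesion rules of 6.3.9 do not define these endpoints.
4. For response confirmation, use the at-least-4-weeks interval of 6.3.1, and point 10.3.2 to 6.3.1 and Appendix E.

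Where these passages govern treatment decisions (3.9.1, 6.3.2, 6.3.9, 6.4.1, Appendix E), the sponsor must reconcile them; no clinical rule is proposed here.

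The cost is a wording amendment, with no extra scans or patients. The target diameters, new-lesion sizes and scan dates needed for both classifications come from the planned assessments. Keeping the nodal tests of 6.3.9 would instead require long-axis measurements that 6.3.3 does not record.

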6.3.10 Time to Progression

Time to progression will be measured from the date of protocol consent until death of progressive disease is documented.

6.3.11 Progression-Free Survival

Progression-free survival (PFS) is defined as the duration of time from the date of study enrollment until time of disease relapse, disease progression, or death, whichever occurs first.

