3.6 POST-TREATMENT EVALUATIONS

Post treatment evaluations (i.e., End of Treatment Visit) will be performed approximately 30 days after the last dose of protocol treatment. If a subject initiates a new anti-cancer therapy within 30 days after the last dose of trial treatment, the 30-day safety follow-up visit must occur before the first dose of the new therapy, if possible. If the patient cannot return to the Clinical Center for this visit, a request will be made to have a local physician or laboratory collect a CBC with differential and send the results. If this is not possible, patients may be assessed by telephone or email for symptoms.

Unless otherwise noted, follow-up will occur at the following time point: every 60 days (\pm 7 days) for 6 months; then every 90 days (\pm 14 days) for 2 years; then every six months (\pm 28 days) for the duration of the study until the start of a new anti-neoplastic therapy, disease progression, death or end of study. Any other evaluations and tests should be performed as clinically indicated.

Upon disease progression or initiation of other anti-cancer therapy, contact will be for survival only until the subject is off study (i.e., every 3 months [\pm 4 weeks]) for the duration of the study. See Study Calendar (Section [APPENDIX F](#)) for additional information. Any adverse events

which are present at the time of discontinuation should be followed in accordance with the safety requirements.

Patients who are removed from study before completing protocol treatment will be followed until completion of the Safety Follow-up Visit or until death, whichever occurs first. Patients removed from study for unacceptable adverse event(s) will be followed until resolution or stabilization of the adverse event.

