6.3 RESPONSE CRITERIA

6.3.1 Response Assessments

Tumor response will be assessed radiographically after cycle 2 and 4 treatments are completed by the investigator using the Immune-Modified Response Evaluation Criteria In Solid Tumors, i.e., imRECIST criteria [\[88\]](#) for Immune-related Best Overall Response (irBOR, Section **6.4.1**) will be derived based on reported lesion responses at different evaluation time points from the first trial treatment administration until immune-related disease progression per imRECIST [\[88\]](#) according to the following rules:

- irCR = at least two radiographic determinations of CR at least 4 weeks apart and before irPD
- irPR = at least two radiographic determinations of PR or better at least 4 weeks apart and before irPD (and not qualifying for an irCR)
- irSD = at least one radiographic assessment of SD (or better) ≥ 6 weeks after the first trial treatment administration and before irPD (and not qualifying for irCR or irPR).
- irPD = at least two consecutive radiographic determinations of PD at least 4 weeks apart.

Only tumor assessments performed before the start of any further anti-cancer treatment will be considered in the assessment of irBOR.

Immune-related Objective Response (irOR) is defined as irCR or irPR according to irRECIST from the first trial treatment administration until irPD or death due to any cause. Both irCR and irPR must be confirmed by repeat assessments performed no less than 4 weeks after the criteria for immune-related response are first met. Also, irPD must be confirmed by a second, consecutive assessment at least 4 weeks apart. Immune-related OR rate (irORR) is the proportion of subjects with irOR in the analysis set.

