6.3.12 Overall Survival

Overall survival (OS) is defined as the time from the date of study enrollment until time of death from any cause.

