6.3.13 Event-Free Survival

Event-free survival (EFS) is defined as the duration of time from the date of study enrollment until time of disease relapse, disease progression, alternative therapy for renal cell carcinoma given (such as radiation), or death, whichever occurs first

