10.4.2 Analysis of Secondary Endpoints

Secondary clinical endpoints of the rate and severity of AEs will be summarized by grade and type of toxicity. The progression-free survival (PFS) and overall survival (OS) will be calculated from the on-study date using the Kaplan Meier method. For PFS and OS, censoring time is defined as time from baseline to date of last follow-up. Duration of response for responders also calculated using the Kaplan-Meier approach is defined as time from the initial response to progression or death, whichever occurs first. Censoring time for duration of response is defined as time from the initial response to date of last follow-up.

The secondary objectives include characterization of biological effects of this treatment and determination of effects of IL-15 on the ADCC capacity of ex vivo PBMCs. These exploratory analyses will be summarized.

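### PFS and duration of response have no rule for new anti-cancer therapy started before progression, so for such patients PFS becomes OS unless progression happens to be captured later

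*Combined protocol and SAP*

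**What the plan says.** - **PFS (6.3.11)** runs "from the date of study enrollment until time of disease relapse, disease progression, or death, whichever occurs first". New therapy is neither an event nor a reason for censoring.
- **OS (6.3.12)** has the same origin: "Overall survival (OS) is defined as the time from the date of study enrollment until time of death from any cause".
- **Censoring (10.4.2)** is one sentence for both: "For PFS and OS, censoring time is defined as time from baseline to date of last follow-up".
- **Duration of response** has two definitions. In 10.4.2 it "is defined as time from the initial response to progression or death, whichever occurs first", censored at last follow-up. In 6.3.8 it ends at objectively documented recurrence or progression, and death is not named.
- **Follow-up (3.6):** "Upon disease progression or initiation of other anti-cancer therapy, contact will be for survival only until the subject is off study". Section 3.6.3 seeks disease status only up to new therapy. Section 3.6.4 moves the patient to survival follow-up at that point whether or not there was progression. In the Appendix F calendar, the survival column lists survival status alone.
- **Where new therapy is handled:** for best response (6.3.1), "Only tumor assessments performed before the start of any further anti-cancer treatment will be considered in the assessment of irBOR". EFS (6.3.13) counts as an event "alternative therapy for renal cell carcinoma given (such as radiation), or death, whichever occurs first". EFS is not among the endpoints in 10.1.

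**The concern.** Counting progression and death regardless of later therapy is a legitimate strategy if scans continue. Here they stop, but the endpoint definitions carry on as if they did not. Time on the next therapy, with no disease assessment, is then credited to the combination as time without progression.

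The route is open in the plan. Protocol therapy ends after at most 4 cycles even in responders (3.1, 3.9.1). Patients who need radiation or other prohibited treatment come off study treatment (4.2). Intolerance, patient request and investigator decision also end treatment without progression (3.9.1).

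At stake are the PFS curve, mainly its tail, and the duration-of-response curve. The latter is the more fragile: 3 responders of 17 is the success threshold (10.2), so one switching responder could be a third of that curve.

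**Working it through.** **The plan's own figures.** No PFS or duration-of-response figure is stated. The figures in 10.2 are for response rate and they reproduce. Early stopping under the null is 0.95^9 = 0.630 (stated 63%). Passing Stage 1 at a 25% rate is 1 − 0.75^9 = 0.925 (stated 92%). The exact two-stage calculation (0/9, then 2/17) gives Type I error 0.0466 and power 0.812. None of this depends on PFS.

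**Reading the rules for one patient.** A patient is progression-free, starts another agent at month 4, and dies at month 18. After month 4 no scan is scheduled. Under 6.3.11 the first recorded event is the death, so PFS is 18 months, the same as OS. If the patient is alive, both are censored at last follow-up. Changing the censoring date alone would not cure this, because the death is an event.

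**Illustrative size.** The inputs are assumptions:
- Median time to progression 5.6 months. This borrows the median PFS of a phase I atezolizumab trial in 1.2.4, which is not this population.
- Median OS 18 months, with death independent of progression.
- A fraction f of patients alive and progression-free at month 4 switch then, unrelated to prognosis.
- Exponential times, no scan-interval delay, no progression captured after the switch.

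Steps:
1. True 12-month PFS = 2^(−12/5.6) × 2^(−12/18) = 0.2264 × 0.6300 = 0.143.
2. Alive and progression-free at month 4 = 2^(−4/5.6) × 2^(−4/18) = 0.6095 × 0.8572 = 0.5225.
3. A switcher stays event-free to month 12 by surviving 8 more months: 2^(−8/18) = 0.7349, and 0.5225 × 0.7349 = 0.384.
4. As written: (1 − f) × 0.143 + f × 0.384, a shift of f × 0.241.

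| f | Share of cohort (0.5225 f) | 12-month PFS as written | Shift |
|---|---|---|---|
| 15% | 7.8% | 17.9% | +3.6 points |
| 30% | 15.7% | 21.5% | +7.2 points |
| 50% | 26.1% | 26.3% | +12.1 points |

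Median PFS moves from 1/(1/5.6 + 1/18) = 4.3 months to at most 4.4. With median OS 12 months and f = 30%, the shift is 0.3 × (0.305 − 0.113) = 5.7 points.

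**Against sampling error.** The PFS set is all patients with at least 1 cycle (10.1.2), and 10.2 has the 2 mcg/kg patients assessed for secondary endpoints. A completed trial therefore has about 3 + 17 = 20 patients, up to the ceiling of 25. The binomial standard error at 14.3% is √(0.143 × 0.857/n): 7.8 points at n = 20 and 7.0 at n = 25. The shift is about half a standard error at f = 15%, about one at 30%, and 1.5 to 1.7 at 50%.

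**If switching is informative.** Suppose instead that 20% of patients switch at a uniform time in months 1 to 4 if still event-free, because they are worsening, with median survival of 3 months afterwards. By the same method, 12-month PFS is 12.9% as written, 14.3% with censoring at the switch, and 11.4% with the switch as an event (0.8 × 0.143). With median survival of 6 months after the switch, it is 15.9% as written, against the same 14.3% and 11.4%.

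**The case against.** **Frequency is unknown.** The documents give no switching rate, and 3.6.3 provides a surveillance phase for patients who finish without progression. This stands: the sizes above are conditional on assumed rates, and at the lowest rate the shift is small against sampling error.

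**The endpoints are secondary.** PFS and duration of response are descriptive in a single-arm study. No test and no 12-month landmark is specified, and the median hardly moves. This also stands, and it limits the importance of the point.

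**Last follow-up could mean last scan.** One sentence covers PFS and OS and does not say so. Even on that reading, a later death remains an event.

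**Progression may still be caught.** Section 6.3.7 asks for every effort to document objective progression after symptomatic deterioration. PFS then differs from OS for that patient, but nothing is scheduled once new therapy begins.

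**Censoring has its own bias.** Section 3.9.1 ends therapy for clinical progression, and 6.3.7 recognises deterioration without objective progression. In the 3-month case above, censoring gives the most favourable of the three estimates. This stands, and it is why censoring should not be reported alone.

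**Stronger readings to avoid.** A reader might infer that these patients have no PFS or duration-of-response value at all. They do: 10.4.2 scores everyone, and what is missing is a rule for new therapy. A reader might also infer that the efficacy decision is compromised. It is not: 6.3.1 already limits best response to assessments before further treatment.

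**Conclusion.** The gap is real and follows from the text. The plan stops looking for progression at new therapy but keeps PFS and the 10.4.2 duration of response running to progression, death or last follow-up. For each affected patient the recorded time is equal to or later than the true one. For a patient whose progression is never captured, PFS is OS.

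Under the non-informative assumptions above, 12-month PFS is raised by about 4 to 12 points when roughly 8% to 26% of the cohort switch. The switching rate, the medians and the independence of switching from prognosis are all assumptions. It should not be claimed that correcting the rule must lower the curve, since informative switching can reverse that. The conflict between 6.3.8 and 10.4.2 over whether death ends a response is a separate defect in the same endpoint. The point is worth fixing before analysis, but it does not threaten the primary conclusion.

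**What to change.** 1. In 6.3.11, 6.3.8 and 10.4.2, state that for PFS and duration of response a patient who starts other anti-cancer therapy, including radiation, before documented progression is censored at the last tumor assessment before that therapy. Later progressions and deaths are not counted.
2. Add EFS, as 6.3.13 already defines it, to Section 10 as the companion analysis in which the switch is an event. For responders, also report duration of response with the switch as an event.
3. Reconcile 6.3.8 with 10.4.2 on whether death ends a response.
4. Report the censored and event versions side by side, with the number of switchers and their reasons.

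The cost is a few sentences and one extra curve for each endpoint. Section 3.6.4 already collects new anti-cancer treatments, so the start date need only be recorded with them. The downside is fewer counted events, and censoring that may be informative when patients switch because they are deteriorating. Neither version should be presented without the other.
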